Study Protocol and Statistical Analysis Plan

Official Title: Messages About Reduced Nicotine in Combusted Tobacco Products

NCT Number: NCT05506046

Document Date: 02/07/2024

Official Title: Messages About Reduced Nicotine in Combusted Tobacco Products

Brief Title: Effects of messages about very low nicotine cigarettes

Sponsor: National Cancer Institute of the National Institutes of Health and the Food and Drug Administration Center for Tobacco Products

Information provided by (Responsible Party): Georgia State University

Collaborator: University of South Carolina

ClinicalTrials.gov Identifier: NCT05506046

Other Study ID Numbers: IRB: H22639

Grant number: R01CA239308

Brief Summary

This randomized controlled trial aims to examine the effects of messages about very low nicotine cigarettes (VLNCs) alone and in combination with messages about e-cigarettes. Previous research on communications about VLNCs has primarily focused on the examination of various textual statements and message attributes rather than fully developed advertisements that are used in real-world communication campaigns. In addition, no research so far has examined the effects of VLNC messages in combination with messages about e-cigarettes, which are the two parallel components of the nicotine-focused regulatory approach. The present study accesses the effects of messages about VLNCs, e-cigarettes, and their combined messaging on perceptions, behavioral intentions, and behavioral outcomes among a nationally representative sample of different smoking status populations.

The study is a four-group RCT with parallel assignment that will be delivered through an online self-administered questionnaire, consisting of two sessions over a two-week period. Participants will be randomly assigned to one of one of four trial arms: 1) VLNC messages, 2) e-cigarette messages, 3) combination of VLNC and e-cigarette messages, and 4) control messages. They will be exposed to 2 messages corresponding to the assigned condition, and answer survey questions immediately after message exposure and two weeks after

Detailed description

The FDA proposed a nicotine-focused regulatory approach to reduce nicotine in cigarettes to non-addictive levels, coupled with advising those who are not ready to quit to obtain nicotine from alternative nicotine delivery products (e-cigarettes). The widespread misperception that very low nicotine cigarettes (VLNCs) are less harmful than regular cigarettes presents challenges in communicating about this policy to the public, especially in a landscape that involves e-cigarettes. This study tested messages about VLNCs alone and combined with e-cigarettes messages that may prepare key population segments for this groundbreaking regulation.

Setting: The trial will be an experiment delivered through an online self-administered questionnaire, consisting of two sessions over a two-week period.

Recruitment: Participants will be recruited through the research company Ipsos from its national research panel (KnowledgePanel).

Informed Consent: Participants will provide online consent prior to taking the survey.

Randomization: After providing informed consent and answer pre-exposure questions, Ipsos will randomize participants into one of the four trial conditions. The randomization will use least fill for the allocation of conditions. In least fill, the survey assigned the condition that had the lowest count. If the counts for the conditions were equal, the survey would assign the condition sequentially.

Assessment: Participants will take part in two sessions: in session 1 (estimated at about 15 min) participants will answer questions assessing smoking status, quit intentions and attempts (only asked adults who smoke exclusively and adults who dual use), e-cigarette use, other tobacco product use, and health literacy. They will then view the messages, and report immediate outcomes including perceptions and behavioral intentions. In session 2, which will take place 2 weeks after session 1, participants will complete a brief 5-minute survey measuring their recall of the messages and behaviors since message exposure.

Study Type: Interventional

Study Phase: N/A

Study Design

Allocation: Randomized

Endpoint Classification: Participant reported outcomes

Intervention Model: Parallel Assignment

Masking: None (open label)

Primary Purpose: Treatment

Condition: Smoking

Intervention

1. Behavioral: exposure to messages about very low nicotine cigarettes (VLNCs)

Two VLNC messages will be drawn at random from a pool of five messages. The messages communicate that VLNCs contain other harmful chemicals and cause diseases just as regular cigarettes, but VLNCs would be easier to quit. Messages will be shown in a random order to participants in the corresponding trial arm in session 1.

2. Behavioral: messages about e-cigarettes

Two e-cigarette messages will be drawn at random from a pool of five messages. The message describes that people who smoke and are not ready to quit could benefit from switching to e-cigarettes to reduce their health risks. They will be shown in a random order to participants in the corresponding trial arm in session 1.

3. Behavioral: combined messaging about VLNCs and e-cigarettes

One message from the pool of VLNC messages and one from the pool of e-cigarette messages will be randomly drawn and shown to the participants during session 1.

4. Other: bottled water ads

Two bottled water ads that have no smoking-related content will be randomly selected from a pool of five messages, and will be shown in a random order.

Study Arm(s)

1. Experimental: VLNC messages
2. Experimental: e-cigarette messages
3. Experimental: combined VLNC and e-cigarette messages
4. Other: control messages (bottled water ads)

Publications: N/A

Recruitment Information

Recruitment Status: Not active

Actual Enrollment: 1901

Actual Completion Date: February 28, 2023

Actual Primary Completion Date: February 28, 2023

Eligibility Criteria

Inclusion Criteria:

1. Being 18 years old or older;
2. Belonging to one of three groups of participants: current exclusive smokers (adults who had smoked at least 100 cigarettes in their lifetime, currently smoked cigarettes every day or some days, and did not use e-cigarettes), dual users (adults who dual use had smoked at least 100 cigarettes in their lifetime, currently smoked cigarettes every

day or some days, and had used e-cigarettes at least once in the past 30 days), and young adult non-smokers (adults aged 18-29 years who had not smoked 100 cigarettes in their lifetime)

3. Enrolled in existing nationally representative panel where recruitment is based

Exclusion Criteria: None

Gender: All

Contacts: [name]. [contact]

Listed Location Countries: United States

Primary Outcome Measures:

Title	Definition	Time Frame
Perceived health risk of VLNCs (absolute)	Measured with a single item, assesses participant's perception of own risk of overall harm to health under conditions of smoking VLNCs every day. Response options range from 1 (Not at all likely) to 5 (Extremely likely) and include "Don't know"	Immediately after exposure

Secondary Outcome Measures:

Title	Definition	Time Frame
Perceived comparative harm of VLNCs	A single item measuring perceptions of comparative risk of smoking reduced nicotine cigarettes vs regular cigarettes. Response options are from 1 (Much less harmful) to 5 (Much more harmful) and include "Don't know."	Immediately after exposure
Perceived absolute addictiveness of VLNCs	A single item measuring participants' perception of likelihood developing addiction to reduced nicotine cigarettes under conditions of smoking them every day. Response options are from 1 (Not at all likely) to 5 (Extremely likely) and include "Don't know."	Immediately after exposure
Interest in trying VLNC	A single item measuring participants' interests in trying VLNC. Response options are from 1 (Not at all) to 7 (Extremely) and include "Don't know".	Immediately after exposure
Intention to switch completely to e-cigarettes	A single item measuring participants' intention to switch completely to e-cigarettes in the next 6 months. Response options are from 1 (Not at all) to 7 (Extremely) and include "Don't know".	Immediately after exposure
VLNC Policy Support	A single item measuring support for the policy to reduce nicotine by 95% in all cigarettes. Response options are from 1 (Strongly Oppose) to 5 (Strongly Support) and include "Don't know."	Immediately after exposure

Perceived Message Effectiveness	3-item scale measuring to what extent participants think the messages they saw discourage them from wanting to smoke, make smoking seem unpleasant, and make them concerned about health risks of smoking. Response options are from 1 (Strongly disagree) to 7 (Strongly agree) and include "Don't know."	Immediately after exposure
Smoking behavior	Single item measuring the average number of cigarettes smoked per day in the past two weeks.	2 weeks after exposure
Perceived absolute health risks of VLNCs at post-test	A single item measuring participants' perception of likelihood developing addiction to regular cigarettes under conditions of smoking them every day. Response options are from 1 (Not at all likely) to 5 (Extremely likely) and include "Don't know." Measured with a single item, assesses participant's perception of own risk of overall harm to health under conditions of smoking reduced nicotine cigarettes every day. Response options range from 1 (Not at all likely) to 5 (Extremely likely) and include "Don't know"	2 weeks after exposure

Analytic Plan

1. Continuous outcomes include the primary outcome (perceived absolute harm of VLNCs), as well as other VLNC-related perceptions and behavioral intentions. Univariate analyses of covariance (ANCOVA) will be used to examine message effects on continuous outcomes.
2. Binary outcomes include smoking and communication behaviors measured at the two-week follow-up survey, as well as quit attempt, cessation, and perceived relative harm of VLNCs. Logistic regression models will be fitted to test binary outcomes.
3. Interaction effects of message conditions and smoking status will be tested by adding interaction terms to the covariate-adjusted models.

Sample size and power

The study intends to recruit a total of 1,800 participants, including 450 participants in each trial condition. It is anticipated that approximately 80% of the participants in session 1 will be retained for the two-week follow-up survey. Given a power set at 80% and a significance level (alpha) of 0.05, the trial has adequate power to detect close to small sized effects, with effect sizes between 0.13-0.28 for continuous outcomes and effect sizes between 1.4-3.5 for binary outcomes.

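### Cigarettes per day is a number, but the plan names two-week smoking behaviors only among its binary outcomes, with no cut and no stated analysis population

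*Combined protocol and SAP*

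**What the plan says.** The Secondary Outcome Measures table defines Smoking behavior, measured two weeks after exposure, as a "Single item measuring the average number of cigarettes smoked per day in the past two weeks". It is the only smoking-behavior outcome in the table.

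Item 1 of the Analytic Plan reads: "Continuous outcomes include the primary outcome (perceived absolute harm of VLNCs), as well as other VLNC-related perceptions and behavioral intentions". These are analysed by ANCOVA. Item 2 reads: "Binary outcomes include smoking and communication behaviors measured at the two-week follow-up survey". It then adds quit attempt, cessation and perceived relative harm of VLNCs, and assigns the group to logistic regression. Item 3 reads: "Interaction effects of message conditions and smoking status will be tested by adding interaction terms to the covariate-adjusted models".

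Three groups are enrolled, one of them "young adult non-smokers (adults aged 18-29 years who had not smoked 100 cigarettes in their lifetime" (Eligibility Criteria). The only restriction to people who smoke is on the session 1 questions about "quit intentions and attempts (only asked adults who smoke exclusively and adults who dual use". For session 2 the Assessment paragraph says only that "participants will complete a brief 5-minute survey measuring their recall of the messages and behaviors since message exposure".

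No section gives a cut, a change threshold, an any/none coding or a count model for cigarettes per day, or says who is analysed for it.

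**The concern.** The outcome is numeric, yet the only item that mentions two-week smoking behaviors treats them as yes/no. Two readings are open.

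- **Item 2 covers cigarettes per day.** The number is then cut at a point the plan does not give. That discards information, and a reader cannot tell how the point was chosen.
- **Item 2 means separate yes/no questions.** Nothing is cut, but cigarettes per day is not clearly assigned to either model.

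On both readings the population is unstated. Non-smokers would probably contribute mostly zeros, though fewer than 100 lifetime cigarettes does not exclude light smoking. Including them changes the estimate and any cut taken from the sample. At stake is the interpretability, and some of the power, of one secondary outcome.

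**Working it through.** **1. The texts side by side.** Outcome table: a number. Item 1: the primary outcome, perceptions and intentions, with no smoking measure named. Item 2: two-week smoking behaviors, binary. Quit attempt and cessation are listed separately in item 2, so they do not supply the missing coding. Item 2 also treats perceived relative harm as binary, although the apparently matching comparative-harm item in the outcome table has five points and again no cut is given. The first reading is therefore credible.

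**2. The plan's power figures.** The plan gives 450 per arm, 80% power, alpha 0.05 (two-sided assumed) and expects that "approximately 80% of the participants in session 1 will be retained for the two-week follow-up survey", so 450 × 0.80 = 360 per arm at two weeks. The detectable standardised difference is d = (1.960 + 0.842) × √(2/n), which is 0.187 at 450 and 0.209 at 360. Both lie inside the stated 0.13-0.28. The endpoints cannot be traced to particular comparisons, and the plan does not say whether the continuous or the binary range applies to cigarettes per day.

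**3. Information kept by a cut on a normal scale.** A cut at quantile p keeps φ(z_p)² / [p(1−p)].
- Median: 0.3989² / 0.25 = 0.637.
- 80/20: 0.2800² / 0.16 = 0.490.

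At 360 per arm and d = 0.209, where the numeric analysis has 80% power, a median cut has about 61% and a cut at the top 10% about 40%.

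**4. Skewed cigarette data.** All inputs here other than 450 per arm and 80% retention are assumptions. The share of people who smoke is taken as 50-80% of 360, so n = 180 to 288 per arm. Detectable drop = 1 − exp[−2.802 × SD × √(2/(n × efficiency))]. For log-normal data, the efficiency of comparing means on the ratio scale is SD²/(exp(SD²) − 1): 0.49/(e^0.49 − 1) = 0.77 at log SD 0.7, and 1/(e − 1) = 0.58 at log SD 1.0.

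| Analysis | Log SD 0.7 | Log SD 1.0 |
|---|---|---|
| Log of the number | 15.1-18.7% | 20.8-25.6% |
| Ratio of means | 16.9-20.9% | 26.4-32.1% |
| Median cut | 18.5-22.8% | 25.4-30.9% |
| 80/20 cut | 20.8-25.6% | 28.4-34.4% |

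At log SD 1.0 with an unlimited tail, a median cut does slightly better than comparing means.

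**5. Simulation.** Rounded log-normal counts, median 9, capped at 60; log SD 0.7 or 1.0; 3% or 10% zeros; with or without heaping at fives; 180 or 240 per arm; 20% drop; unadjusted; 4,000 trials in each of 16 settings.
- Power: ratio of means 0.38-0.85, median cut 0.32-0.77, 80/20 cut 0.28-0.66.
- Loss within a setting against the ratio of means: 5.5-9.1 points (median cut) and 9.5-20.8 points (80/20 cut). Slightly different cut and heaping rules gave about 6-11 and 10-25 points.
- Without the cap (log SD 1.0, 3% zeros, 240 per arm, no heaping): 0.48 for the ratio of means and 0.47 for the median cut, so almost no loss.
- A plain comparison of means, as in ANCOVA, has about the same power as the ratio of means.
- Log(c+1) reaches 0.58 in that last setting, about 11 points above the median cut, but with 10% zeros it falls behind the ratio of means. No numeric model is best throughout.

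**6. Population.** Suppose one third of those followed are non-smokers reporting zero (assumed; the plan gives no split). The overall median then sits at (0.5 − 1/3)/(2/3) = the 25th percentile among people who smoke. A cut there keeps φ(z_0.25)²/(0.25 × 0.75) = 0.3178²/0.1875 = 54% if smoking status is adjusted for. Pooled and unadjusted, it keeps (2/3) × 0.3178²/0.25 = 27%. In a numeric analysis the same zeros would shrink the mean difference to two thirds of its value among people who smoke.

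**The case against.** The best defence is that neither list claims to be exhaustive; both use the word include. Item 2 names matters absent from the outcome table, such as communication behaviors, which fits separate yes/no questions. The ANCOVA sentence is general to continuous outcomes, so cigarettes per day could fall under it by default. This stands in part: a reader might infer that the whole analysis of this outcome is open to choice, and that goes too far. It does not remove the ambiguity, because item 1 omits the outcome, item 2 names smoking behaviors, and the population is missing either way.

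The defence can also say that the loss depends on assumed spread, zeros, heaping and tail, and may be negligible at a median cut. That stands. It also means the documents do not support requiring a negative binomial or other count model in place of the plan's own ANCOVA.

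Two other inferences are tempting:
- **The item 3 interaction will fail.** An interaction term cannot be estimated by ordinary logistic regression if no non-smoker in some arm exceeds the cut. That needs the first reading, no restriction to people who smoke, and a near-zero share above an unknown cut. Nothing in the documents fixes that share.
- **The cut was picked from the data.** The document is dated 02/07/2024 and data collection ended February 28, 2023, but it does not say when this analysis was fixed. The dates neither show a data-driven choice nor rule one out.

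**Conclusion.** The concern holds in a limited form. The textual gap is certain: a numeric secondary outcome is named, if at all, only among the binary outcomes, without a cut and without an analysis population. The cost is conditional on item 2 covering it. Against a comparison of means, the power loss at a median cut is nearly none to about 9 points under the assumed distributions, and larger at an 80/20 cut with the assumed cap (about 10 to 21 points). If item 2 means separate yes/no questions, no power figure applies and the fault is unclear assignment. The primary outcome is unaffected. The point is worth correcting because the remedy is cheap and gives a defined estimate in a defined population.

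**What to change.** Move cigarettes per day from item 2 to the continuous outcomes in item 1. Analyse it as a number among exclusive smokers and dual users by ANCOVA, adjusted for smoking status and for baseline consumption if that is held, with robust standard errors. Add a log or count model as a sensitivity analysis for skew and zeros. If the session 2 item was put only to people who smoke, say so.

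Keep logistic regression for quit attempt, cessation and any other genuinely yes/no items, and list those items. If a cut of cigarettes per day is reported, state the cut and present it as secondary. State when the analysis of this outcome was fixed, and label as post hoc anything chosen after the data were seen, including this model.

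The cost is revised wording and one small reanalysis of data in hand, with no new data collection. The downside is carrying the post hoc label.

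### Does restricting non-smokers to ages 18-29 undermine the planned test of message condition by smoking status?

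*Combined protocol and SAP*

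**What the plan says.** Analytic Plan, item 3: "Interaction effects of message conditions and smoking status will be tested by adding interaction terms to the covariate-adjusted models". The item does not define the levels of smoking status, list the covariates or mention age.

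The levels come from the Inclusion Criteria. The general age criterion is "Being 18 years old or older". Item 2 then names three groups: current exclusive smokers, dual users and "young adult non-smokers (adults aged 18-29 years who had not smoked 100 cigarettes in their lifetime". Only the third has an upper age limit. No other status groups are enrolled, so reading item 3 as referring to these three is an inference, but a safe one.

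Two passages describe the aim. The Brief Summary speaks of effects "among a nationally representative sample of different smoking status populations", without repeating the age limit. The Detailed description speaks of "messages that may prepare key population segments for this groundbreaking regulation", which is language about segments.

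**The concern.** Item 3 is the only planned test of whether message effects differ between groups, and its label is broader than the group it describes. A reader who sees an interaction with smoking status may conclude that not smoking changes the response to the messages, when being under 30 could explain some or all of the difference. The same reader may extend the result to non-smokers aged 30 and over, who were not eligible.

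The reference to covariate-adjusted models looks like protection but is not. An age main effect shifts outcome levels by age. It leaves the condition-by-status coefficient free to absorb any change in the message effect with age. The omnibus interaction is affected as well, because it includes the non-smoker level.

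The point bears mainly on perception and intention outcomes, because some behavioural items were never put to non-smokers. The session 1 questions include "quit intentions and attempts (only asked adults who smoke exclusively and adults who dual use".

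**Working it through.** The plan gives no figure for this comparison, so there is none to reproduce. The structural claim is settled by reading the Inclusion Criteria beside item 3: one level is capped at 29, two are uncapped, and no condition-by-age term is planned. The arithmetic below only illustrates size.

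**Inputs.** From Sample size and power: 450 per arm and alpha 0.05 (taken as two-sided). Assumed, because the documents do not give them:
- equal thirds, so 450/3 = 150 per group per arm;
- a share s of each smoking group under 30, taken as 0.10, 0.15 or 0.25;
- a message effect of 0.30 SD under 30 and 0.10 SD otherwise, with no true effect of status.

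**Difference produced by age alone.** This is d_young − [s·d_young + (1 − s)·d_old] = (1 − s)(0.30 − 0.10):
- s = 0.10: 0.90 × 0.20 = 0.18
- s = 0.15: 0.85 × 0.20 = 0.17
- s = 0.25: 0.75 × 0.20 = 0.15

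**Non-smokers against one smoking group.** SE = √(4/150) = 0.163. The detectable difference at 80% power is 2.802 × 0.163 = 0.457 SD. Differences of 0.18, 0.17 and 0.15 are declared in 19.7%, 18.0% and 15.1% of trials, against a nominal 5%.

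**Non-smokers against both smoking groups pooled.** SE = √(2/150 + 2/300) = 0.141. The detectable difference is 0.396 SD. Declared in 24.7%, 22.5% and 18.6%.

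**Omnibus interaction (4 × 3; 6 and 1,788 df).** If one message arm, or all three equally, carries the age-varying effect, noncentrality is 2.43, 2.17 and 1.69, and rejection is 17.1%, 15.5% and 12.9%. If two arms carry it, noncentrality is 3.24, 2.89 and 2.25, and rejection is about 22%, 20% and 16%.

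**Sensitivity to the assumptions.**
- With effects of 0.20 and 0.10 SD, the age-only difference is 0.09 to 0.075 SD. It is declared in 8.5% to 7.4% (one group) or 9.8% to 8.3% (pooled).
- With 40-50% of smokers under 30 and effects of 0.30 and 0.10 SD, the difference is 0.12 to 0.10 SD. It is declared in about 11% to 9% (one group) or 14% to 11% (pooled).
- With no change in effect by age, the difference is zero and the test keeps its level.

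**Does an age covariate help?** In 1,000 simulated trials, smokers were aged uniformly 18-75, non-smokers 18-29, and the effect changed by 0.01 SD per year with no status effect. With age as a main effect only, the interaction was declared in 35.5% of runs; with a slope of zero, in 5.1%. Adding condition by age gave 3.8% and restricting to ages 18-29 gave 6.2%, with the mean interaction near zero (0.01 SD) in both. A main effect therefore does not separate age from status.

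**What an 18-29 analysis would deliver.** Pooled smokers under 30 per arm: 300 × s = 30, 45 or 75. SE = √(2/150 + 2/n), where n is that number of young smokers.

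| Young smokers per arm | SE | 95% half-width | Detectable difference | Power for 0.30 SD |
|---|---|---|---|---|
| 30 | 0.283 | 0.55 | 0.79 | 18.6% |
| 45 | 0.240 | 0.47 | 0.67 | 23.9% |
| 75 | 0.200 | 0.39 | 0.56 | 32.3% |

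Against a single smoking group (15 to 37.5 per arm), power is 12.3% to 21.3%. Ages would also have to be available from panel or survey data. The Assessment paragraph lists smoking status, quit items, "e-cigarette use, other tobacco product use, and health literacy", but not age.

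**The case for a change.** The best case for a change is that this imbalance is created by the eligibility rule. It is not the ordinary correlation between traits that comes with any non-randomised modifier. The analytic plan replaces a narrow group with a general label, the wording about covariate adjustment may give false comfort, and a few words plus one descriptive model would guard against a misattributed subgroup claim.

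The facts in that argument stand. Age and status are mixed by design in every non-smoker contrast, and an age main effect does not undo it.

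The remedy does not follow. The corrective wording is already in Inclusion Criteria item 2, and an analytic plan need not restate eligibility in each item. The feared misreading would arise in a later report; the plan itself makes no causal statement about status. The extra model would usually be inconclusive. It could not attribute a difference to status, which is not randomised, and pooling smokers would drop the exclusive/dual distinction that the plan draws. One model would also become several contrasts across several outcomes, including intention to switch completely to e-cigarettes, where comparing non-smokers with smokers has doubtful meaning. The record shows "Actual Completion Date: February 28, 2023" and the document is dated 02/07/2024, so the addition would probably be post hoc.

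**Conclusion.** No change to the plan is needed. Smoking status in item 3 is shorthand for the three recruited groups, and the test answers the question it can answer: whether message effects differ between those groups. Randomised message effects overall and within each group are untouched, and the exclusive-smoker versus dual-user contrast has no built-in age restriction.

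What remains is a limit on interpretation. A difference involving non-smokers is a difference between segments, and it does not reach non-smokers aged 30 and over. Analysts who use the label in the eligibility criteria will report it that way without an amendment.

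An age contribution of 0.15-0.18 SD, declared in roughly 15-25% of trials for a single contrast, depends wholly on an assumed group split, an assumed share of young smokers and an assumed threefold age gap in message effect. Milder assumptions bring the rate down to about 7-14%, and with no age modification it is the nominal 5%. These figures are in SD units and do not cover outcomes analysed by logistic regression, which item 2 of the Analytic Plan says include perceived relative harm. The documents give no basis for choosing among these values.
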